Alcohol dependence (alcoholism) and insomnia in Veterans occur at rates that are 2-7 times higher than that of the general population. Further, there is evidence that insomnia is a significant risk factor for relapse in abstinent alcoholics. Given these findings, it is surprising that very little research has been conducted to determine whether: the insomnia that occurs with military experiences and/or withdrawal abates with time; the incidence or severity of insomnia is associated with the clinical course of alcoholism; targeted treatment for insomnia during withdrawal is effective; and positive treatment response for insomnia is associated with duration of remission and/or risk for relapse during abstinence. From the few studies that exist, the following tentative claims can be made: 1) alcoholism severity is associated with insomnia severity^{1,2}; 2) insomnia is a risk factor for relapse³⁻⁵; 3) short-term treatment of insomnia during first year of recovery improves sleep continuity via reduction in both time to fall asleep and time awake during the night. While the results from these studies are promising, most investigations were conducted in small samples (all but two studies had final samples of < 20 subjects)^{6,7} and were populated by patients with poorly-defined alcohol and insomnia phenotypes (e.g., family history, age of onset, duration of illness, illness severity, type and subtype of insomnia [e.g., psychophysiologic insomnia, idiopathic insomnia, paradoxical insomnia and/or initial, middle, late, or mixed insomnia]). Further, most of the studies did not have follow-ups that evaluated the durability of the insomnia treatment⁸⁻¹⁰ and how this was related to occurrence of relapse or other alcohol-related measures (e.g., alcohol craving, number of drinks per day, the occurrence of binge drinking, etc.). In order to address some of these limitations, we propose to conduct a study of standard Cognitive Behavioral Therapy for Insomnia (CBT-I) in 60 alcohol-dependent Veterans during the first year of their recovery. CBT-I was selected as the treatment modality for several reasons. First, CBT-I produces treatment outcomes that are as large, or larger than pharmacotherapy in patients with Primary Insomnia^{11,12}, and there is a growing body of evidence suggesting that it is as effective in Secondary Insomnia¹³⁻¹⁵. Second, unlike pharmacotherapy, CBT-I

exhibits durable results following treatment discontinuation^{16,17} and less likely to interact with medications being used for replacement therapy or management of comorbid illness. Third, there are three small-scale studies with CBT-I showing that the regimen is applicable in the context of alcoholism (i.e., subjects comply with/ benefit from the treatment)^{8,9,18}.

Chronic insomnia has been associated with high-frequency EEG activity (β and γ , 16-50 Hz), a measure of cortical arousal. In addition, there is a diminished δ and increased high-frequency NREM EEG power among patients with insomnia, as well as an association between high-frequency EEG activity and subjective sleep complaints. High-frequency EEG enhances sensory and information processing, which may contribute to the subjective-objective discrepancy that often characterizes insomnia. Evidence is mixed regarding insomnia-control differences in high-frequency EEG activity during wakefulness. However, high-frequency waking EEG activity significantly correlates with high-frequency EEG activity during NREM and with self-reported hyperarousal symptoms. These findings support the hypothesis that high-frequency EEG power in insomnia is a marker of CNS hyperarousal. On a preliminary basis, we will investigate the role of CBT-I treatment in decreasing the cortical arousal in these patients.

Purpose of the Project:

Insomnia is classified as both a primary disorder and a symptom of other disorders in DSM IV. In the DSM V insomnia will be classified as a primary disorder (i.e., as "Insomnia Disorder") when it occurs in isolation and as a co-morbid disorder when it occurs as a consequence of another medical and psychiatric illnesses. There are three major implications of this paradigmatic shift. First, as a disorder (vs. a symptom secondary to a primary illness), it can no longer be assumed that the "cause" of the insomnia is the primary disorder and that treatment for the primary disorder will result in a resolution of the insomnia. Second, as a co-morbid disorder, insomnia can be conceptualized as co-occurring condition that may interact with other disorders and thus result in greater illness severity in one or both conditions. Third, as a co-morbid disorder, insomnia occurring with other disease states may complicate the treatment of the co-occurring condition (i.e., result in reduced treatment efficacy), and/or the occurring condition will complicate the treatment of the insomnia.

These implications are directly applicable to the insomnia that occurs in association with alcoholism and give rise to the following questions. First, is there evidence that insomnia is a risk factor for the first episode of alcoholism (suggesting that insomnia occurs before and not as a result of the alcoholism). Second, data show that alcoholism severity is greater in patients with insomnia as compared to patients without insomnia and (conversely) that insomnia severity is greater in patients with alcoholism as compared to patients without alcoholism (suggesting that the two disease states interact as independent disorders to reciprocally confer greater morbidity). Third, there is evidence that insomnia complicates the treatment of alcoholism and/or that chronic alcoholism is associated with perpetuation of insomnia (suggesting targeted treatment for both disorders is required when they occur co-morbidly).

Given the newness of the paradigmatic shift, it comes as no surprise that none of the above questions have been addressed in a manner that allows for definitive answers. What is known is that insomnia is highly prevalent in patients with alcoholism, and there are preliminary data to suggest that 1) insomnia is a risk factor for recurrence of alcoholism; 2) alcoholism severity is greater in patients with insomnia as compared to patients without insomnia; and 3) targeted treatment for insomnia in the context of alcoholism diminishes insomnia severity.

Showing that CBT-I is an effective method for managing insomnia in the context of alcoholism will provide clinicians with an additional treatment option for the millions that suffer from insomnia comorbid with alcoholism. Demonstrating that the clinical course of patients with alcoholism is significantly improved by targeted treatment for insomnia will allow for a new and better standard of care and will open a new research window into "how and why" sleep disturbance interacts with the predisposition for, and severity of, alcoholism.

I. **Describe the Research Questions or Hypotheses**

Specific Aim 1 (Primary Aim): Determine the efficacy of standard 8-week CBT-I intervention in recovering alcohol dependent subjects. Hypothesis 1: Alcohol dependent participants who receive CBT-I, compared to the QDT, will exhibit greater improvement on the ISI and more durable treatment gains on follow-up at 3 and 6 months. Secondary analyses will assess for group differences in sleep continuity (e.g., average SL, WASO, and TST) over all time points and will evaluate these parameters relative to the meta-analytic norms.

Specific Aim 2: Investigate whether the alcohol dependent Veterans treated with CBT-I have reduced recidivism compared to those in the QDT control condition. Hypothesis 2: Alcohol dependent participants who receive CBT-I, compared to QDT, will exhibit a significantly higher percentage of days abstinent. Secondary analyses will assess for group differences on other alcoholism-related outcomes (e.g., craving, drinks per drinking day, and proportion of heavy drinking days).

Specific Aim 3: Evaluate if subjects treated with CBT-I have a greater improvement in daytime functioning as compared to subjects in the QDT. Hypothesis 3: Alcohol-dependent participants treated with CBT-I will exhibit greater improvement in subjective daily functioning (health-related quality of life [primary end point]), as well as anxiety and depressive symptoms [secondary end points]).

Exploratory Aim(s): Assess the potential relevance of genetic and neurobiologic factors as predictors of illness severity and treatment outcome. Specifically, family history of alcoholism and actigraphic data will be acquired during the course of the proposed project and evaluated for their relevance as correlates of clinical course.

J. **Primary Outcome Variable(s):**

- a) The primary sleep outcome measure for the study is the insomnia severity (as assessed with the Insomnia Severity Index scale (ISI)^{19,20};
- b) The primary alcohol outcome measure is percentage days abstinent (as assessed using the Timeline Follow Back measure (TLFB)²¹⁻²⁶).

K. **Secondary Outcome Variable(s):**

- a) The secondary sleep outcome measures are the traditional five sleep continuity values that are obtained from the daily sleep diaries (averaged as weekly values for sleep latency [SL], number of awakenings [NWAK], wake after sleep onset [WASO], total sleep time [TST] and SE%); other outcome measures will include Pittsburgh Sleep Quality Index (PSQI), Composite Scale of Morningness (CSM), Knowledge Assessment Questionnaire (KAQ), the Treatment Evaluation Questionnaire (TEQ), and pre- and post-treatment evaluation questionnaire, Columbia-Suicide Severity Rating Scale Baseline version (CSSR-B) & Columbia-Suicide Severity Rating Scale Follow-up Screener (CSSR-S-FS), and the Epworth Sleepiness Scale (ESS). In a subset of subjects the polysomnographic sleep variables (sleep onset latency, sleep efficiency, wake after sleep onset time) will also be evaluated.
- b) The secondary alcohol measures are alcohol craving (assessed with Penn Alcohol Craving Scale, PACS)²⁷⁻³⁰, number of drinks per drinking day, and percent of heavy drinking days (assessed with the TLFB)²²⁻²⁶, Short Index of Problems (SIP).
- c) The outcome measures for health and mood are the Short Form-12 item scale (SF-12)³¹, the Patient Health Questionnaire 9-item scale (PHQ9)^{32,33}, the Generalized Anxiety Disorders 7-item scale (GAD7)^{34,35}, the Beck Depression Inventory-II scale (BDI-II)^{36,37} and the State-Trait Anxiety Inventory (STAI)³⁸, Columbia Suicide Severity Rating Scale (C-SSRS-B), and the Barratt's Impulsivity Scale (BIS), Interpersonal Support Evaluation List (ISEL), and Addictions Severity Index (ASI), Columbia-Suicide Severity Rating Scale Baseline version (CSSR-B) & Columbia-Suicide Severity Rating Scale Follow-up Screener (CSSR-S-FS).
- d) Family History of Alcohol Dependence will be assessed using the Semi Structured Assessment of the Genetics of Alcoholism (SSAGA) – Family History Assessment Module (FHAM)^{39,40}.
- e) Other drug use will be assessed using the SCID-I module for abuse and dependence on other drugs⁴¹ as well as with a Urine Drug Screen (UDS). See Figure 1 and Table 1 for details.

L. Study Design and Methods:

1. Is this a clinical trial? YES NO
- 1.1. If yes, what type? Check all that apply. N/A
 Phase I Phase II Phase III Phase IV
- 1.2. If yes, this study must be registered on Clinicaltrials.gov.

2. Design

- 2.1. What research methods will be used in the project? Check all that apply.

 Surveys/Questionnaires	 Interviews	 Audio Taping
 Behavioral Observations	 Chart Reviews	 Video Taping
 Focus Groups	 Randomization	 Double-Blind
 Control Group	 Placebo	 Withhold/Delay Treatment
 Specimen Collection	 Deception	 Telephone Survey
 Other (Describe)		

Eight Session CBT-I: General Protocol. Cognitive Behavioral therapy is conducted in 8 sessions during which subjects meet individually with the study clinician. Session 1 serves as an orientation. No active treatment is delivered at this time. Sessions 2 & 3 are used to deliver the three main components of the intervention which are Sleep Restriction (SRT)^{42,43}, Stimulus Control⁴⁴⁻⁴⁶, and Sleep Hygiene⁴⁷⁻⁴⁹. All but two of the remaining sessions are dedicated to the titration of total sleep time and to ensuring patient adherence. One session (session 5) entails the delivery of a specific form of cognitive therapy. The cognitive element targeted in this session is modeled on Barlow's approach to the cognitive restructuring of catastrophic thinking as it occurs in insomnia with panic disorder. This approach was adapted to address the catastrophic thinking as it occurs in insomnia in relation to the consequences of poor sleep. The final session (session 8) is used to engage in a relapse-prevention didactic, i.e., to review first, how insomnia becomes chronic and second, the strategies that are likely to abort an extended episode of insomnia. The specific details for each of the above interventions (e.g., titration rules, stimulus control rules, etc.) and itineraries for each of the individual sessions are detailed in the Penn treatment manual (published by Springer in 2005 [hardback] and re-printed in 2008 [paperback])⁵⁰.

Quasi-Desensitization Placebo Therapy (QDT). This form of placebo therapy has been commonly used in prior studies investigating behavioral interventions for insomnia^{9,13,51,52}. The therapist presents the QDT as a means to eliminate "conditioned arousal," occurring after nocturnal arousal using 8 sessions on a weekly basis. The therapist initially helps the subject to develop a chronological 12-item hierarchy of commonly practiced activities on awakening at night, like opening eyes and clock watching. As a next step, the subject develops 6 imaginal scenes of himself/herself engaged in neutral activities like reading a newspaper. The therapist then helps the subject pair the neutral scenes with the items from the 12-item hierarchy, which is then practiced by the subject ≥ 2 hours before bedtime.

- 2.2. Describe how randomization or other treatment assignment will be made. **Subjects will be block randomized using a computer generated randomizing sequence.** Participants are randomly assigned to the CBT-I group, or the QDT group. The study biostatistician will create randomization sequences by family history of alcoholism (separate sequences) using a pseudo-random number generator with block sizes of 4. Two boxes of sequentially numbered, sealed, opaque envelopes will be prepared using the randomization sequences and labeled "Family History" and "No Family History". At the time of randomization, the first envelope, in sequential order, is pulled from the appropriate box and opened to reveal the group assignment. All the staff conducting assessments will be blinded to the allocation of treatment arm with the exception of Dr.

[name], the BSM treatment provider, [name] the person overseeing treatment allocation, and [name], the monitor for BSM treatment for the study.

- 2.3. For retrospective research studies, provide the "look-back" period. (e.g., December 1, 1999 through December 31, 2008.) **N/A.**

3. **Study Duration**

- 3.1. Provide the estimated length of time to enroll all subjects and complete the study. **Five years.**
- 3.2. Explain the expected duration of subject participation including any follow-up. **Eight months.**
- 3.3. Specify the projected date of completion of the proposed study. **Dec. 2018.**

4. **Drug Information.** Not Applicable.

5. **Investigational Device.** Not Applicable.

M. **Does this project involve international research?** YES NO

N. **Study Procedure.** Please see Table 1 for all the study-related procedures.

The actigraph: A wristband that the patient wears on his/her non-dominant arm continuously over a 1 week period, measures rest/activity as a surrogate marker for sleep and wakefulness). Actiwatch® (Mini Mitter Company) recordings will be obtained to measure duration of nocturnal inactivity as a proxy for sleep duration during simultaneously recorded, time-linked Stardust II® recordings. Estimated sleep time, the primary actigraph outcome measure, will be used to calculate the total sleep time and quality of sleep at home. Actiwatch® is a compact, wrist-worn, battery-operated activity monitor that utilizes a motion sensor known as an "accelerometer" to monitor the occurrence and degree of motion. Actiwatch® is programmed to collect data using the Sleepwatch software application that runs on an IBM-compatible PC. A sleep diary will be filled out by the subject while using the actigraph. The sleep diary is a subjective log maintained by the subject of the times he falls asleep and awakens over the 24-hour period. The sleep diary filled out by the subject (on the days of the actigraph use) will be used to assess and clarify the sleep wake data as measured by the actigraph. The actigraphy will be done at baseline and during the treatment study weeks. Conduct of the actigraphy during the post-treatment follow-up at 3- and 6-month visits will be deemed optional.

Overnight in-laboratory polysomnography (PSG): a registered polysomnographic technologist will perform the overnight polysomnographic sleep studies at the CMCVAMC sleep center. The polysomnograms will include electroencephalography, electromyography, electrooculography, electrocardiogram, pulse oximeter, and plethysmography to monitor for chest muscle activity. Overnight polysomnograms will be performed using standard techniques (12). The following signals will be recorded using a computer data acquisition and analysis system (Mallinckrodt, Pleasanton, CA): electroencephalogram (C3A2 and O2A1), bilateral electrooculograms, chin muscle activity, bilateral anterior tibialis electromyogram, rib cage and abdominal movement, nasal pressure and snoring (Pro-Tech, Woodinville, WA), body position, and heart rate and oxygen saturation by pulse oximetry (Ohmeda, Louisville, CO). The PSG will be conducted in a subset of up to 20 subjects (up to 10 in the CBT-I arm and up to 10 in the QDT arm) in an equitable distribution across both treatment arms and pending availability of funds. Each subject will have complete 2 PSG studies, one at baseline and one at the end of treatment (within weeks 7-8 of the treatment visits).

1.1. Outline all study procedures.

Table 1: A List of Assessments Involved with Participation in this Study

Table 3. Data Collection Table													
Scales		Baseline	Treatment-Related Visits								Post-Study		
			W1	W2	W3	W4	W5	W6	W7	W8	F/U 1	F/U 2	
Sleep	SDS-CL												
	Type III Monitor												
	ISI												
	ESS												
	Sleep Diary												
	Actigraphy												
	PSQI												
	CSM												
	KAQ												
	TEQ												
	EQ												
	Therapist Checklist												
	Alcohol	Polysomnogram											
SCID-I													
SSAGA-FHAM													
CIWA													
UDS													
SIP													
TLFB													
PACS													
Psychiatr	Breathalyzer												
	SCID-I												
	BOMC												
	C-SSRS-B												
	BIS												
	PHQ-9												
	BDI-II												
	STAI												
GAD-7													

Acronyms
 Type III Monitor = Type III portable sleep monitor
 PSG = Polysomnography
 PSQI = Pittsburgh Sleep Quality Index,
 CSM = Composite Scale of Morningness,
 KAQ = Knowledge Assessment Questionnaire,
 TEQ= Treatment Experience Questionnaire,
 EQ=BSM Expectancy Questionnaire;
 ISI = Insomnia Severity Index,
 SCID- = Structured Clinical Interview for DSM-IV-TR Axis I Diagnoses,
 SSAGA-FHAM = Semi-structured Assessment for the Genetics of Alcoholism,
 CIWA = Clinical Institute Withdrawal Assessment for Alcoholism scale,
 UDS = Urine Drug Screen,
 SIP – Short Index of Problems Scale,
 TLFB = Time Line Follow Back,
 PACS = Penn Alcohol Craving Scale,
 BOMC = Blessed Orientation Memory Concentration test,
 C-SSRS-B = Columbia Suicide Severity Rating Scale – Baseline version
 PHQ9 = Patient Health Questionnaire 9-items,
 BDI = Beck Depression Inventory,
 STAI = State Trait Anxiety Inventory,
 GAD7 = Generalized Anxiety Disorders-7 Questionnaire,
 PCL-S = PTSD Checklist - specific
 QOL = Quality of Life,
 SF-12 = Health-Related Quality of Life, Short Form 12,
 TBI Screener = Traumatic Brain Injury Screener,
 ESS = Epworth Sleepiness Scale
 ASI = Addictions Severity Index
 ISEL = Interpersonal Support Evaluation List
 C-SSRS-FS = Columbia Suicide Severity Rating Scale – Follow-up Screener version
 W = Week #,
 F/U = Follow up visit.

patient's electronic medical record if one was done during the time the patient is undergoing the baseline assessment period; d) Blood sample - will be drawn up and processed by [name], or the designated staff member associated with the study, including the study coordinator after IRB approved training and at the CMCVAMC laboratory services as a back-up option; e) Overnight polysomnography will be done at the CMCVAMC sleep center by their credentialed sleep technicians. [name] will serve as a back-up staff member for any of the study-related procedures.

- 1.4. **If a survey study, specify the estimated amount of time that subjects will need to complete the questionnaires/tools.** N/A
- 1.5. **If a blood draw, specify the amount of blood to be drawn in milliliters and in teaspoonful or tablespoonful and specify how often and where the blood will be drawn.** About one tablespoon (~15ml).

2. **Data Collection**

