4.1. **Include statistical power calculations and the assumptions made in making these calculations.** The following power calculations for Aims 1-3 assume the availability of 86 subjects who are eligible for randomization into one of two groups (n=43 per group). We assume a range of intra-class correlation of 0.1-0.5 and up to 10 follow-up measures per participant. The sample size is inflated to accommodate a 30% missing or dropout rate by 6 months based on rates over a similar period of time in previous studies⁵⁵. We consider a conservative adjustment in the two-sided level of significance, 0.025, to account for two hypothesis tests per Aim (3-month and 6-month outcome). Table 4 presents the detectable effect size based on the above assumptions for 90% and 80% power. The study will have 80% power to detect a moderate effect size of 0.50 standard deviations of a continuous outcome measure at 6 months assuming an intra-class correlation of 0.3. Table 5 presents the detectable effect in units applicable to each outcome based on the observed standard deviation from studies in the literature.

Power	Intra-class Correlation	Detectable effect size	
		3 months	6 months
80%	0.1	0.35	0.40
	0.3	0.48	0.50
	0.5	0.58	0.61
90%	0.1	0.40	0.41
	0.3	0.55	0.57
	0.5	0.66	0.70

(Assumptions: power=80%; n=30 per group after 30% attrition; 2-sided=0.05)

- Standard Deviation
- Insomnia Se
- Quality of Life
- Pooled within group standard deviation
- Pooled within group standard deviation (estimated from presented data)
- Pooled within group standard deviation for general health

Outcome	Pre-Post S.D. ^a	Detectable Difference
ISI ^b	3.809 ^d	1.90 points
Abstinent Days	15.96 ^e	7.98 %
Health Related QOL ^c	9.15 ^f	4.58 points

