model. In this model, the mean ISI depends on fixed covariates and random effects⁵⁷. The fixed covariates of interest include time, treatment assignment, the interaction between time and treatment assignment, adjusting for family history of alcoholism and confounding variables identified in the preliminary analysis. The random effects represent the unobserved factors that lead to variation of the individual participant's outcome. Random intercepts for each participant permit modeling of natural variation across participants at baseline in the outcome of interest. In addition, random slopes or random effects for the trajectory of each participant over time allow for variation of each participant about a mean, overall trajectory across all participants. Estimates of the random effect for an individual participant also permit far more focused investigations of those individuals who depart from the mean over time and experience either better or worse than average change in outcome. Thus, the mixed effects longitudinal model permits both comparisons of groups as well as contrasts of individuals. Although less robust to model misspecification, the mixed effects paradigm offers special flexibility in longitudinal data when exposures vary over time and when dropout and missed visits lead to unbalanced groups. ISI and quality of life are continuous measures and most likely follow a symmetric or approximately normal distribution. Therefore the linear mixed regression model is appropriate. If departures from normality are found, we will consider transformations or other distributional forms that may better fit the data. The alcoholism-related outcome measures are counts (e.g. number of days abstinent, number of heavy drinking days, etc.) but will be summarized as percentages (e.g. percent abstinent days) and will also most likely follow a normal distribution. The target of inference is the participant-specific response to treatment over time. Specifically we are interested in the efficacy at the end of treatment (8 weeks) and durability after 3 and 6 months of follow-up. At each time point of interest, we will estimate from the fitted model the difference from baseline in the outcome for each treatment group and test the difference between these differences. The treatment effects will be the contrasts that represent the difference of differences from baseline in outcome across treatment groups at 3 and 6 months. Both univariate and multivariate results will be reported in terms of Wald test, point estimates, and 95% confidence intervals.

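### Section I names one Primary Aim (insomnia severity), but section J lists two primary outcomes and the 0.025 level protects each aim separately, so if either outcome may carry the trial the false-positive chance is about 8-10%, not 5%

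*Combined protocol and SAP*

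**What the plan says.** All places are in the combined protocol and SAP.

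- **Section I** marks one aim as primary: "Specific Aim 1 (Primary Aim): Determine the efficacy of standard 8-week CBT-I intervention". Its hypothesis concerns ISI. Aim 2 (percent days abstinent) and Aim 3 (daytime functioning) do not carry that label.
- **Section J**, the list of primary outcome variables, has two entries. Item a: "The primary sleep outcome measure for the study is the insomnia severity". Item b: "The primary alcohol outcome measure is percentage days abstinent", which is the Aim 2 outcome.
- **Hypothesis 3** in section I tags "health-related quality of life [primary end point"] against secondary end points for anxiety and depression. **Section K**, item c, lists the SF-12, the quality-of-life instrument, among the secondary outcomes.
- **Section V, item 4.1** sets the level: "We consider a conservative adjustment in the two-sided level of significance, 0.025". The reason given is "to account for two hypothesis tests per Aim (3-month and 6-month outcome").
- **Section V, item 4.2** analyses Aims 1-3 in parallel with one type of mixed model and defines the treatment effects as the "difference of differences from baseline in outcome across treatment groups at 3 and 6 months".

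No section orders the aims, requires success on both primary outcomes, or divides the error rate between them.

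**The concern.** The plan accepts that several tests call for adjustment, but stops at the boundary of each aim. Two outcomes carry the word primary in section J and only one aim carries it in section I, so the headline result is not defined. Suppose ISI shows nothing and percent days abstinent crosses 0.025 at 6 months. Going by section I, the primary aim has failed. Going by section J, one of two primary outcomes has succeeded. Both reports could cite the protocol, and the choice could be made after the data are seen. The 5% error rate held within an aim would then not apply to the claim actually made.

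**Working it through.** **1. The plan's own level.** Two tests per aim: 0.05 / 2 = 0.025. To check that the power table uses it, take the detectable effect as

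d = (z for 1 - α/2 + z for power) × √{2[1 + (m - 1)ρ] / (m n)}

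with n = 30 per group after attrition, ρ = 0.3 and 80% power. The number of measures m behind each cell is not stated; the plan says up to ten.

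- α = 0.025, m = 10: (2.241 + 0.842) × √(2 × 3.7 / 300) = 3.083 × 0.157 = 0.484. The plan gives 0.48 at 3 months.
- α = 0.025, m = 8: 3.083 × √(2 × 3.1 / 240) = 0.496. The plan gives 0.50 at 6 months.
- α = 0.05, m = 10: 2.802 × 0.157 = 0.440, which does not match.

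So 0.025 is the working level, although a note beside the power tables gives two-sided 0.05. Within one aim, the chance of a false positive is 1 - 0.975² = 4.9% if the two tests are independent, and 4.3% if they correlate 0.7. The adjustment does its job inside an aim.

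**2. The labels side by side.**

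| Outcome | Section I | Section J | Section K |
|---|---|---|---|
| ISI | Primary Aim | primary | - |
| Percent days abstinent | Aim 2, no primary label | primary | - |
| Quality of life (SF-12) | lead end point of Aim 3 | not listed | secondary |

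The conflict concerns percent days abstinent.

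**3. Two outcomes at two time points, each at 0.025, no true effect.** If all four tests are independent: 1 - 0.975⁴ = 9.6%. The upper bound is 4 × 0.025 = 10%. The documents give no correlations between tests, so these are assumed, and the rates come from simulated correlated normal test statistics:

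| Correlation, 3 vs 6 months | Outcomes independent | Outcomes correlated 0.2 |
|---|---|---|
| 0 | 9.6% | 9.6% |
| 0.5 | 9.1% | about 9.1% |
| 0.7 | 8.4% | 8.3% |
| 0.9 | 7.1% | 7.0% |

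**4. Does testing abstinence after ISI restore 5%?** That depends on what counts as ISI being met.

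- *Either time point opens the gate.* Let ISI have a strong true effect at one time only, with no effect on abstinence. The gate is then almost always open and three null tests remain: 1 - 0.975³ = 7.3% if independent, 6.7% at a time-point correlation of 0.7. The 5% level is not held.
- *Both time points must be significant.* If ISI is null at one or both times, abstinence is reached only after a false ISI rejection, so the error stays within the ISI allowance of at most 5%. If ISI is truly effective at both, only the two abstinence tests can err, at most 2 × 0.025 = 5%. The level holds in every case.
- *Cost of the stricter gate.* With 80% power at each time, it opens with probability 0.8 × 0.8 = 64% if independent, and 71% at a correlation of 0.7.

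**The case against.** The strongest reply is that primary here means the lead measure within a domain. Sections J and K use domain labels (sleep, alcohol), and the hypotheses, models and level adjustment are all organised by aim. On that reading Aim 1 is the primary aim, its error is held at 5%, and Aim 2 answers a separate question. Whether to adjust across separate questions is partly convention, and section S, item 3 calls this a pilot study. The plan nowhere says that success on any one outcome makes the trial positive. This much stands: the 8-10% is conditional on such a claim being made, and the plan does not commit itself to it. What does not stand is that the reading settles the matter. Section J presents abstinence as a primary outcome without qualification, item 4.1 powers formal tests for all three aims, and no text says which outcome decides.

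A reader might also infer from Hypothesis 3 that there are three primary outcomes and six tests, with an error of 12-14%. The documents do not support that. Section J omits quality of life, section K files the SF-12 as secondary, and the tag in Hypothesis 3 ranks measures within Aim 3.

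**Conclusion.** The point holds for two outcomes. Sections I and J disagree on whether percent days abstinent is a primary outcome of the trial, and the 0.025 level does not reach across outcomes. If success on either were reported as a positive primary result, the chance of at least one false positive would be about 8-10%, falling to about 7% when the 3- and 6-month tests correlate 0.9, against at most 5% within an aim. The figures assume no effect on either outcome, two-sided tests at 0.025, and the stated correlations. They count only the 3- and 6-month contrasts; the 8-week contrast, also named as of interest in item 4.2, lies outside the 0.025 split and is not included. The analysis models themselves are not invalidated. What is missing is a statement of which result decides the trial, and this should be corrected before analysis.

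**What to change.** In section J, name ISI as the single primary outcome, in line with the Primary Aim label, and repeat in item 4.2 that it is tested at two-sided 0.025 at each of 3 and 6 months. This holds 5% and leaves ISI power as planned. Relabel percent days abstinent as the key secondary outcome, and report its estimates and intervals whatever ISI shows.

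If a confirmatory claim on abstinence is wanted, add that it is tested, at 0.025 per time point, only if ISI is significant at both 3 and 6 months. A gate opened by either time point should not be used, for the reason in step 4 of the working.

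The cost is wording in section J and item 4.2. The downside is that an abstinence result without an ISI result is supportive only, and the both-time-points gate would open only about 64-71% of the time at 80% power per test. If both outcomes must stay primary, the level can be split over four tests, 0.05 / 4 = 0.0125. Anchored on the plan's 80% power for 0.50 SD, power per test falls to about 72% (3.083 - 2.498 = 0.585 on the normal scale) and the effect detectable with 80% power rises to about 0.54 SD.
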